To evaluate the durability of the efficacy of satralizumab versus placebo in the AChR+ population and the OP	Duration (average number of consecutive months) of meaningful improvement, defined as ≥ 2-point reduction from baseline in total MG-ADL score a

AChR = acetylcholine receptor; AChR+ = AChR-antibody seropositive (patients/population); ADA = anti-drug antibody; AUC = area under the concentration–time curve; CL/F = apparent clearance;  $C_{trough}$ = trough concentration; gMG= generalized myasthenia gravis; IL-6=interleukin-6; MG=Myasthenia gravis; MG-ADL= Myasthenia Gravis Activities of Daily Living; MGC= Myasthenia Gravis Composite; MG-QOL 15r= Myasthenia Gravis Quality of Life 15 Scale (revised); NCI CTCAE v5.0 = National Cancer Institute Common Terminology Criteria for Adverse Events, Version 5.0; Neuro–QoL = Quality of Life in Neurological Disorders; OP = overall population; PD = pharmacodynamic; PK = pharmacokinetic; QMG = Quantitative Myasthenia Gravis; QoL = quality of life; sIL-6R = soluble interleukin-6 receptor; V/F = apparent volume of distribution.

<sup>a Patients who receive rescue therapy will be considered non-responders

Table 2 Objectives and Endpoints during the Double-Blind Period (cont.)

Exploratory Efficacy Objectives	Corresponding Endpoints

 
To evaluate the efficacy of satralizumab versus placebo in the AChR+ population and OP on:
 
	

 
Severity of gMG exacerbations
 
	
 
Severity of gMG-related exacerbations
 
Proportion of patients with at least one gMG-related exacerbation leading to hospitalization between baseline and Week 24
 
Annualized rate of gMG-related exacerbations leading to hospitalization
 

– Time-to-event	
 
Time to disease improvement as measured by:         
 
≥ 2-point reduction in total MG-ADL score or
 
≥ 3-point reduction in QMG score or
 
≥ 3-point reduction in total MGC score or
 
MG-ADL score of 0 or 1
 
 
 
Time to disease worsening as measured by the time from baseline to:         
 
Start of rescue therapy
 
gMG-related exacerbation
 
Hospitalizations related to gMG exacerbation
 
 
 

– QoL	Mean change from baseline to Week 24 in EuroQoL EQ-5D-5L Health Utility Index score
Safety Objective	Corresponding Endpoints

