## 6.4.7 Duration Estimand and Estimator

The elements of the duration estimand are defined below using the AChR + population as an example:

- Population: Patients with AChR+ gMG as defined by the study inclusion and exclusion criteria
- Secondary efficacy variable: Number of consecutive visits when a patient achieved a ≥ 2-point reduction from baseline in MG-ADL, without receiving rescue therapy
- Treatment: satralizumab 120 mg (for patients with body weight ≤ 100 kg) or 180 mg (for patients with body weight > 100 kg) versus matching placebo, administered for 24 weeks, in combination with stable background therapy

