4.2.5 Supplementary Analyses for Primary Endpoint(s)

In addition to the primary analysis for each efficacy score at Week 24, the same analysis will be performed for each other clinical visit date: Week 2, Week 4, Week 8, Week 12, Week 16 and Week 20.

Subgroup analyses for the primary endpoint will be performed to explore whether the treatment effect on the primary endpoint is consistent across subgroups. The influence of baseline and demographic characteristics on the treatment effect among participants will be explored via exploratory subset analyses for the following factors:

- Sex
- Age at diagnosis
- Race
- Region
- Background therapy
- Baseline disease severity and characteristics
- Dose level.

Treatment effects within each subgroup will be examined separately using the imputed data of the primary estimand and the model specified previously for the primary endpoint.

Forest plots will be generated displaying the estimated difference (the effect size of the primary treatment effect), 95% confidence intervals, and the corresponding p-value for each subgroup, with the overall result also included at the bottom. These subsidiary analyses are intended to provide reassurance that the observed treatment effect is consistent across all participant subgroups.

The study is not powered to detect differences between subgroups and any observed patterns should be interpreted extremely cautiously, owing to the smaller numbers and increased chance of type I error.

All listed subgroup analyses will be presented in a forest plot showing the effect size of the primary treatment effect in that subgroup.

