4.3.4 Secondary Endpoints Under the Duration Estimand

The duration estimand is only relevant for the analysis of the number of consecutive visits a participant shows an MG-ADL reduction of at least 2 points from baseline. Based on the completed data set, the first time a participant shows a 2-point or more reduction from baseline, the duration is measured until Week 24 or until the visit when MG-ADL=is no longer reduced by 2 points from baseline MG-ADL. The duration is the difference in weeks between the two visits defining the start and end (or Week 24) of reduction from baseline. If the participant shows a reduction for only one visit, the count is set to 1 week. If the participant required rescue therapy, the count is stopped prior to the visit at which the participant received rescue therapy (composite).

The count variable (the number in weeks by consecutive visits) will be modeled using an ANCOVA adjusting for the same covariates as the imputation model and baseline MG-ADL. The treatment effect estimator is the regression coefficient of the treatment group. The estimate is the difference in the mean duration of meaningful improvement at Week 24.

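### The duration endpoint stops at the first lapse and ignores later runs, so an extra early response can sharply lower a participant's durability score

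*SAP*

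**What the plan says.** The rule is in SAP 4.3.4 and works on the completed (imputed) data set.

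- **Start:** "the first time a participant shows a 2-point or more reduction from baseline, the duration is measured until Week 24".
- **Other stopping point:** "or until the visit when MG-ADL=is no longer reduced by 2 points from baseline MG-ADL".
- **Arithmetic:** "The duration is the difference in weeks between the two visits defining the start and end (or Week 24) of reduction from baseline".
- **One-visit rule:** "If the participant shows a reduction for only one visit, the count is set to 1 week".
- **Rescue:** counting stops before the visit at which rescue was given.

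The result, in weeks, goes into an ANCOVA, and the estimate is the difference in mean duration. Nothing in the section restarts the clock, adds later runs or takes the longest run.

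Protocol Section 2 (Table 2) names the endpoint "Duration (average number of consecutive months) of meaningful improvement" and ties it to the durability objective. Protocol 6.4.7 defines the variable as "Number of consecutive visits when a patient achieved a" reduction of 2 points or more without rescue, and does not say which run counts. SAP Appendix 1 lists only the split into MMRM imputation and ANCOVA as a change from the protocol.

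**The concern.** A durability score should not fall when a participant responds at more visits. Under this rule it can. One early response followed by a lapse fixes the score, and any later sustained response is discarded. Protocol 1.1 describes the disease as fluctuating, so an isolated early response and lapse is an expected pattern.

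The one-visit rule raises a second, smaller question. Whether it fits the difference rule depends on which visit ends a run, and the text does not settle that.

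At stake is the precision and meaning of the only secondary endpoint assigned to the durability objective.

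**Working it through.** The documents give no expected duration, SD or power for this endpoint, so there is no planned figure to reproduce. The check applies the rule to the visit schedule and then illustrates its size.

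**1. Visits.** SAP 4.2.5 lists "Week 2, Week 4, Week 8, Week 12, Week 16 and Week 20"; Week 24 completes the double-blind schedule.

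**2. The rule on single participants (weeks).**

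| Response pattern | SAP score | Longest run |
|---|---|---|
| Week 2 yes, Week 4 no, Weeks 8–24 yes | 1 | 24 − 8 = 16 |
| Weeks 8–24 yes only | 24 − 8 = 16 | 16 |
| Week 4 yes, Week 8 no, Weeks 12–24 yes | 1 | 24 − 12 = 12 |

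The first two rows differ only in the added Week 2 response, which takes the score from 16 to 1.

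The score of 1 reads the one-visit sentence as applying to the scored run. If it applies to the whole double-blind period, the first participant (six response visits) falls under the difference rule instead:
- End at the first non-response visit: 4 − 2 = 2 weeks.
- End at the last response visit: 2 − 2 = 0 weeks.

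The 16 later weeks are lost on every reading.

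**3. The end visit.**
- *First non-response visit:* a run at Week 8 only, lost at Week 12, spans 12 − 8 = 4 weeks but is set to 1. A run at Weeks 8 and 12, lost at Week 16, scores 16 − 8 = 8.
- *Last response visit:* the Week 8 run spans 8 − 8 = 0, so the 1-week rule is a floor. The two-visit run scores 12 − 8 = 4.

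**4. All patterns.** Seven visits give 2^7 = 128 yes/no patterns. In 57, a one-visit first run is followed by a later run. Measured to the last response visit, the longest run is at least 8 weeks in 12 of these, at least 12 weeks in 4, and 16 weeks in 1. These are counts of patterns, not probabilities.

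**5. Simulated size.** From SAP 2.2: mean improvements of 4.3 and 2.3 points, SD 3.97, 80 per arm. Assumed, because the documents do not give them: SD 3.97 at every visit, correlation 0.7–0.9 per 4 weeks, visit-level noise SD 0–2 points, no rescue, and a mean that is either flat or rises linearly to its Week 24 value by Week 12. Over 18 scenarios:
- 6–20% of responders are scored on a run that is not their longest.
- 3–8% of responders have a run of at least 8 weeks ending at Week 24 but a one-visit first run.
- Power is about 2–17 points lower than with the longest run, in the same direction every time. With a flat mean the loss is at most about 9 points; the larger losses come from the linear rise.
- The 1-week rule alone moves power by about 2 points or less.
- The mean difference between arms agrees within about 0.25 weeks.

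**6. Mean difference under another correlation structure.** Equal correlation between all visits, linear rise to Week 12, end at the last response visit; mean weeks, satralizumab minus placebo:

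| Correlation | First run | Longest run |
|---|---|---|
| 0.5 | 9.61 − 6.40 = 3.21 | 11.76 − 7.98 = 3.78 |
| 0.7 | 10.88 − 7.56 = 3.32 | 12.52 − 8.93 = 3.59 |
| 0.9 | 12.79 − 9.30 = 3.49 | 13.65 − 10.18 = 3.47 |

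The gap between the two scores is 0.57, 0.27 and −0.02 weeks, so it is small except at the lowest correlation.

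**The case against.** **Time from first response to first loss is a coherent variable.** It is pre-specified and applied identically in both arms, and the protocol does not say which run it means. A reader might infer that the SAP contradicts the protocol. It does not; it settles an open point. What remains is that the choice is neither justified nor flagged, and it serves a durability objective poorly.

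**The one-visit rule may simply be a floor.** A reader might infer that it breaks the SAP's own definition. That holds only if the end is the first non-response visit. The stop rule points that way, but the last-response reading makes the rule sensible. The supportable criticism is ambiguity. The exact score of 1 week in the example also depends on a reading.

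**The endpoint carries little inferential weight.** This stands. It is not among the eight confirmatory endpoints in SAP 4.3.7, and no power is claimed for it. Sustained responders also appear in the Week 24 responder analysis and the by-visit analyses.

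**The mixed units are editorial.** This stands too. Months, visits and weeks all appear as labels, but SAP 4.3.4 defines the analysed variable in weeks, and SAP Section 1 says the SAP supersedes the protocol for filings.

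**Conclusion.** The first-run restriction is a real weakness of a supportive endpoint. On any reading, one extra early response can cut a score from 16 weeks to between 0 and 2. The consequence is added noise: roughly 2–17 points of power against the longest-run score. The direction was consistent, but the size rests on assumed correlation, visit noise and time course, none of which the documents supply. Most of the loss comes from ignoring later runs; the 1-week rule contributes little.

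A reader might infer that the rule biases the comparison against satralizumab or threatens the trial's main conclusion. Neither is supported. The mean difference changes little in most scenarios, and the primary result, the hierarchy and type I error are untouched.

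**What to change.** Before unblinding, amend SAP 4.3.4 as follows:

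- Define the variable as the longest rescue-free run of visits with an MG-ADL reduction of at least 2 points.
- State one end-visit rule, for example the first non-response visit, or Week 24 if response continues.
- Apply that rule to every run, including one-visit runs, so that a run at Week 8 only, lost at Week 12, scores 4 weeks.
- Keep a minimum of 1 week. Otherwise a first response at Week 24 scores 24 − 24 = 0, the same as never responding.
- Keep the first-run score as a sensitivity analysis.
- List the change in SAP Appendix 1 and use weeks in the endpoint tables.

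The cost is SAP wording and a small change to the derivation, with no new data. The downside is that the variable differs slightly from the one now specified, which the sensitivity analysis makes visible.

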4.3.5 Secondary Endpoint of Rescue Therapy

The endpoint of proportions of participants receiving rescue therapy during the double—blind period will analyze the variable that encodes whether a participant received rescue therapy during the double-blind period or not. Treatment policy is used, that is if a participant stops study drug but receives rescue therapy during the safety follow-up and this occurs within 24 weeks of baseline then this is counted as having received rescue therapy. Stop of study drug and no further information available will be imputed as not having received rescue therapy.

A Cochran-Mantel-Haenszel test over the treatment groups stratifying for baseline stratification factors is the treatment effect estimator for the proportions of participants receiving rescue therapy. The estimate is the difference in proportion at Week 24.

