4.2.1.2 Intercurrent Events for the Primary Estimand

In this section, we will discuss specifically how ICEs are categorized and approaches for handling missing data due to ICEs.

In this study, three different ICEs are considered:

- · Withdrawal from study treatment
- Receiving a rescue therapy
- Treatment interruption due to infection.

As described in Table 5, the ICEs are classified into two main categories:

- Study Drug or Condition Related ICE (SDCR ICE)
- Not Study Drug or Condition Related ICE (NSDCR ICE).

For the generic ICE "Withdrawal from study treatment" information on the cause and categorization into whether the interruption is SDCR or NSDCR is collected in the electronic Case Report Form (eCRF):

- NSDCR: Pregnancy, study terminated by Sponsor
- SDCR: Adverse Event (AE), death, lack of efficacy
- NSDCR or SDCR: Lost to follow-up, protocol deviation, withdrawal by subject, physician decision, other.

The last bullet collects cause that the investigator will be asked for categorization into NSDCR or SDCR in the eCRF.

Depending on to the classification of ICEs, we propose estimand strategies and statistical imputation methodology in handling SDCR- and NSDCR-ICEs in Table 5.

 Table 5
 Handling of ICEs for the Primary Endpoint

Intercurrent Event Classification	Study Drug or Condition Related (SDCR)	Not Study Drug or Condition Related (NSDCR)
Intercurrent event	Withdrawal from study treatment (AE, death, lack of efficacy). ¹ Lost to follow-up, protocol deviation, withdrawal by subject, physician decision and other, that are specified for the individual participant as SDCR. Receiving a rescue therapy. ² Treatment interruption due to infection. ³	Withdrawal from study treatment (Pregnancy, study terminated by Sponsor). Lost to follow-up, protocol deviation, withdrawal by subject, physician decision, other., that are specified as NSDCR for the individual participant.
Estimand Strategy	Treatment Policy In the treatment policy strategy, the occurrence of SDCR ICE is ignored and measurements of the variable of interest are used as such. In other words, the analysis does not make any statistical adjustment for SDCR ICE.	Hypothetical Approach The hypothetical approach envisages a scenario wherein it is presumed that NSDCR ICE would not have occurred. Thus, assumes that NSDCR ICE did not happen in the participants who consented to participate.

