Data Collection	Regardless of ICE occurrence, the participant will be ask endpoint and data collection will continue as long as poss	ed to remain in the study to be evaluated for the primary efficacy sible.
Data Strategy	Data are used as available to estimate a treatment effect irrespective of the occurrence of SDCR ICE. This assumption will estimate the treatment effect by analyzing outcomes as they were observed, assuming rescue therapy is part of the standard treatment regimen and hence data are considered as recorded.	All data after an ICE is ignored.

Table 5 Handling of ICEs for the Primary Endpoint

Intercurrent Event Classification	Study Drug or Condition Related (SDCR)	Not Study Drug or Condition Related (NSDCR)
Imputation Strategy	If data are unavailable, or only partial data are available subsequent to a SDCR ICE, then data are used as available and the remainder is imputed using copy reference. Data are imputed using copy reference methodology (i.e., data are imputed from the placebo arm). The underlying assumption being that participants who discontinue the active arm did not get a benefit from the proposed treatment after the SDCR ICE. In other words, the participant profile following SDCR ICE tracks that of the reference arm but starting from the benefit already obtained.	Data are imputed using a missing at random assumption that is data will be imputed conditional on observed data. The imputation under a missing at random assumption estimates a treatment effect as if the ICE had not happened.

¹ For the generic ICE "Withdrawal from study treatment" information on the cause and categorization into whether the interruption is study drug or condition related (SDCR) or not SDCR (NSDCR) is collected in the electronic Case Report Form.

If a participant has recorded multiple ICEs, then the category of the first ICE will determine the handling strategy of all subsequent missing data.

² Receiving rescue therapy might not result in a treatment interruption but is a relevant ICE in this study that always falls under the SDCR category.

 $^{^{\}rm 3}$ Treatment interruption due to infection will always be categorized as SDCR.

The precise statistical imputation methodology is detailed in section on missingness and imputation.

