4.3.7 Hierarchy of Secondary Endpoints

The primary and secondary endpoints will be tested using a hierarchical gatekeeping procedure. Where the hierarchical gatekeeping procedure is used, if any test result is not statistically significant, formal testing of subsequent endpoints will not occur. If the primary endpoint is statistically significant, the confirmatory secondary endpoints are tested in the following order:

- 1. Mean change from baseline in QMG score in AChR+ participants at Week 24
- Mean change from baseline in MG-QOL 15r total score in AChR+ at Week 24
- 3. Mean change from baseline in MGC total score in AChR+ participants at Week 24
- 4. Mean change from baseline in MG-ADL score in the OP at Week 24
- 5. Mean change from baseline in QMG score in the OP at Week 24
- 6. Proportion of AChR+ participants receiving rescue therapy between baseline and Week 24
- 7. Mean change from baseline in MG-ADL score in MuSK+ and LRP4+ at Week 24
- 8. Mean change from baseline in Neuro-QoL Fatigue Subscale total score in AChR+ participants at Week 24.

4.3.8 Software for Computation of Primary and Secondary Endpoints Analysis

The implementation of the previous described analyses will be conducted using the programing language R. The estimand framework will be implemented using the rbmi package. The statistical analysis will be conducted using the programing languages SAS and R.

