4.4.2 Additional Evidence of Efficacy

4.4.2.1 Time to Disease Improvement and Disease Worsening

Time-to-event analyses of the following endpoints will be conducted on mITT participants during the double-blind period.

Time to disease improvement (composite endpoint):

- ≥2 point reduction in total MG-ADL score
- ≥3 point reduction in QMG score
- ≥3 point reduction in MGC score
- MG-ADL score of 0 or 1 (minimal symptom expression status)
- Combination (whichever happens first) of reduction by ≥2 points in total MG-ADL or ≥3 points in total QMG score

Time to disease worsening:

- Time to first use of rescue therapy
- Time to MG-related exacerbation.

Participants with no event during the double-blind period will be censored on the day of their last double-blind period visit. The time of each event will be derived from the actual time point the event first occurs compared to the timepoint of baseline. The first four endpoints will use a composite strategy for rescue therapy, i.e., participants will be coded as not having had an event if they receive rescue therapy during the double-blind period and they will be censored at the time they receive rescue therapy. The treatment effect will be estimated using a log-rank test. Kaplan-Meier curves will be used to plot the data and listings will contain survival estimates at regular time points.

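### Rescue therapy endpoint (confirmatory step 6): unknown status after stopping study drug is always filled in as not rescued, and no sensitivity analysis tests this

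*SAP*

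**What the plan says.** SAP 4.3.5 codes each participant as rescued or not during the double-blind period and compares arms with a stratified Cochran-Mantel-Haenszel test on the difference in proportions. It names a treatment policy strategy. Rescue after stopping drug counts, since the section includes the case "if a participant stops study drug but receives rescue therapy during the safety follow-up and this occurs within 24 weeks of baseline". If nothing more is known, "Stop of study drug and no further information available will be imputed as not having received rescue therapy". Neither sentence distinguishes by arm or reason.

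SAP 4.3.7 lists "Proportion of AChR+ participants receiving rescue therapy between baseline and Week 24" as step 6 of eight confirmatory secondary endpoints, under the rule that "if any test result is not statistically significant, formal testing of subsequent endpoints will not occur". Steps 7 and 8 therefore depend on it.

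Other parts of the plan treat the same withdrawals differently:

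- SAP 4.2.1.2 fixes some reasons as always related to drug or condition: "SDCR: Adverse Event (AE), death, lack of efficacy". For the scores, missing satralizumab data after such an event are imputed by copy reference: "The underlying assumption being that participants who discontinue the active arm did not get a benefit from the proposed treatment after the SDCR ICE".
- SAP 4.4.2.1, for the exploratory time to first rescue: "Participants with no event during the double-blind period will be censored on the day of their last double-blind period visit".

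Protocol 6.4.4 places the rescue proportion outside the estimand framework, and the protocol gives no missing-data rule for it. The analyses in SAP 4.2.4 (rescue, protocol deviations, tipping point) concern the primary endpoint only.

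**The concern.** Treatment policy settles which observed data are used. It does not justify a definite value when nothing was observed. Here the value is always the favourable one. It is given even to participants who left because treatment was not working, who may be among those likeliest to need rescue.

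An arm with more unfollowed withdrawals therefore gets a lower rescue proportion through loss of information alone. The fill is also a single value carrying no uncertainty, so the test treats unknowns as if they had been observed. A formal claim on step 6, and access to steps 7 and 8, could turn on this without the reader being able to see it.

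**Working it through.** **Inputs.** SAP 2.2 (same figures in Protocol 6.1): 80 AChR+ participants per arm; planned rescue about 10% satralizumab and 20% placebo; treatment withdrawal 10%, not split by arm, reason or availability of follow-up; changes of 4.3 and 2.3 points (difference 2.0); SD 3.97; two-sided α 0.05; 85% power. No power is stated for the rescue endpoint.

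**1. The plan's own figure.** n per arm = 2(z₀.₉₇₅ + z₀.₈₅)² SD²/δ² = 2 × (1.960 + 1.036)² × 3.97²/2.0² = 70.7, so 71. Dividing by 0.90 gives 79 per arm, 158 in total, against 160 stated. It reproduces.

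**2. How many can be affected.** 10% of 160 is 16, or 8 per arm if evenly split. Reaching that would need every withdrawal to be unfollowed. Each participant moves an arm's rate by 1/80 = 1.25 percentage points.

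**3. Power for rescue at 10% v 20%, 80 per arm.** Under the null, SE₀ = √(2 × 0.15 × 0.85/80) = 0.0565. Under the alternative, SE₁ = √((0.20 × 0.80 + 0.10 × 0.90)/80) = 0.0559. Power = Φ((0.10 − 1.96 × 0.0565)/0.0559) = Φ(−0.19), about 42%.

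**4. How few participants matter.** Pooled two-proportion z = (p₁ − p₂)/√(p̄(1 − p̄)(2/80)), an unstratified approximation to the planned test.

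| Satralizumab v placebo, of 80 each | Difference (points) | z | p |
|---|---|---|---|
| 8 v 16 (planned rates) | 10.0 | 1.77 | 0.077 |
| 7 v 16 | 11.25 | 2.03 | 0.043 |
| 9 v 16 (two more on satralizumab) | 8.75 | 1.52 | 0.127 |

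If two of the satralizumab participants filled in as not rescued had in fact been rescued, 7 v 16 becomes 9 v 16 and significance is lost.

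**5. Direction.** Start from 8 v 16 recorded rescues. Under the SAP rule the result is p = 0.077 however many unknowns there are. Now count 16 unknowns as rescued, with the arm split assumed:

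| Unknowns, satralizumab / placebo | Counts | Difference (points) | p |
|---|---|---|---|
| 8 / 8 | 16 v 24 | 10 | 0.144 |
| 12 / 4 | 20 v 20 | 0 | 1.00 |
| 4 / 12 | 12 v 28 | 20 | 0.003 |

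The rule can help or harm satralizumab.

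**6. False-positive illustration.** Suppose true need for rescue is 20% in both arms, and 4 of 80 would-be rescues on satralizumab go unobserved, with none lost on placebo. Expected rates are then 15% v 20%, SE₀ = √(2 × 0.175 × 0.825/80) = 0.0601 and SE₁ = √((0.16 + 0.1275)/80) = 0.0599. The chance of a result favouring satralizumab is Φ((0.05 − 1.96 × 0.0601)/0.0599) = Φ(−1.13), about 13% instead of 2.5%. The same loss on placebo would favour placebo equally.

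**The case against.** The strongest reply is that the rule reaches few people. It applies only when nothing further is known. Participants who stop drug are asked to complete all remaining assessments, or otherwise an end-of-treatment visit within 4 weeks and a follow-up visit at 12 weeks (Protocol 3.1.6, 4.6.1). Appendix 1 footnote e adds 4-weekly telephone interviews, and concomitant medication is recorded at both visits. This stands, and it is why 8 per arm is a ceiling. It does not remove the gap. The interviews are specified to detect neurological symptoms, not rescue use. For adults who decline visits they also end 12 weeks after the last dose, so a last dose before Week 12 leaves time before Week 24 uncovered.

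Three stronger readings are tempting, and the documents do not support them.

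- *Every withdrawal for lack of efficacy, and every death, becomes a success.* Recorded rescue within 24 weeks still counts. A participant who dies with no recorded rescue had no recorded rescue. Whether death should count as failure is a question about the endpoint, not an imputation error.
- *The SAP contradicts itself.* Copy reference is a rule for the longitudinal scores, and the censoring rule belongs to an exploratory log-rank analysis. The protocol puts this endpoint outside the estimand framework. The plan is less cautious here than elsewhere, but not inconsistent.
- *The rule inflates the satralizumab effect.* If satralizumab works, lack-of-efficacy withdrawals should be commoner on placebo, and the rule would then count against it. Examples that put all hidden rescues on satralizumab are selective: 6 v 18 (p = 0.008) becomes 10 v 18 (p = 0.096) with four added there only, but 10 v 22 (p = 0.018) with four added in each arm.

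The SAP version 3 change table also mentions a low number of rescue administrations, without giving it. The planned 10% and 20% may not describe this trial.

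**Conclusion.** The point holds in a limited form. SAP 4.3.5 scores unknown rescue status after stopping drug as favourable whatever the reason, on a confirmatory endpoint, and nothing planned tests that choice. The number affected should be small, at most the planned 10% withdrawals, and the net direction cannot be known in advance. It matters because the comparison has little power at the planned rates (about 42%), so two participants can move the result across 0.05.

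The p-values rest on 80 per arm, an unstratified test and assumed numbers and arm splits of hidden rescues, since the documents give none. They show how sensitive the test is; they do not predict the result. This is an inexpensive improvement that should be made, and it does not affect the primary analysis.

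**What to change.** 1. In SAP 4.3.5, replace the single not-rescued fill with a rule that depends on the withdrawal reason. For example, use multiple imputation of unknown status: after a withdrawal related to drug or condition, from the placebo-arm rescue risk over the weeks remaining to Week 24, in line with copy reference for the scores; after an unrelated withdrawal, under missing at random.
2. Prespecify one sensitivity analysis for this endpoint. Either count related withdrawals with unknown status as rescued, with deaths without recorded rescue shown separately in a composite of rescue or death; or run a tipping-point analysis that varies the number of unknowns counted as rescued in both arms.
3. Ask about rescue use at the existing 4-weekly telephone contacts and record the answer.

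Kaplan-Meier estimation with censoring would drop the certain fill, but it assumes that loss is unrelated to the need for rescue, which is the assumption in doubt. It would not be enough alone.

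Cost: SAP wording, a little more analysis and one added question per call. The estimate may move in either direction, and its interval will be slightly wider. Sample size and treatment are unchanged.
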